### **3.c.5. Data Monitoring Plan**

Data management and data entry will be conducted by the investigative team, who will establish a participant tracking and data monitoring system. Research assistants will be trained in interviewer-administered instruments (e.g., SCID, LIFE, THI) at [REDACTED] using established procedures. RAs complete follow-up assessments and will be blind to intervention condition. All assessments will be audiotaped and reliability checks for RA-administered interviews will be made monthly throughout the study.

Data will be collected using standardized paper forms or (if collected by telephone or zoom) will be directly entered into a REDCap database, and will only be identified with the study's ID of the participant. REDCap is a secure, web-based application developed by Vanderbilt University for building and managing surveys and databases. REDCap is designed to support online or offline data capture for research studies, quality improvement, and operations. REDCap provides easy data manipulation (with audit trails for reporting, monitoring, and querying participant records), real-time data entry validation and an automated export mechanism to common statistical packages.

The codes that link the name of the participant and the study ID will be kept confidential by [REDACTED] in a secured cabinet. Collected forms will be transported to [REDACTED] data entry center. Data quality will be monitored by random inspection of the completed forms by one of the research assistants and any problems detected will be discussed with the PI. Standard data checking procedures will include checking forms for missing data, daily back-up copies of computer files, and examination of key variables for skewness, variability, missing data, and outliers. Study statistician [REDACTED] will analyze the data using SAS or SPSS.

The computer systems used for data entry and analysis are protected by passwords and secure logon and data communications procedures to minimize the potential for disclosure of research information either inadvertently or as a result of external attack. Within each computer system, only those users authorized to access the data for a given study are able to do so. Research records are stored in areas that are locked when staff is not present.

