Those assigned to receive the CARE intervention (n= 12 in the open trial; n = 20 in the pilot randomized trial) will be invited to have a family member or significant other (heretofore referred to as SO) participate in the intervention with them. We highlight that this is not a requirement for participation of the prisoner participant, but will be optional. Hence, we will enroll up to 32 SOs into this study. In order to be eligible for participation, SOs must be over 18, speak and read English, have frequent (at least every other week) contact with the prisoner participant, be on the prisoner participant's visitor list at the [REDACTED] (for those prisoners recruited while still incarcerated), and consent to participate in treatment.

Finally, as part of the treatment development process, we will conduct brief (~30 min) stakeholder interviews with relevant parties (e.g., [REDACTED] staff and administrators, community mental health partners). We anticipate conducting up to 6 interviews with relevant stakeholders (2 each with [REDACTED] staff, administrators, and partnered community mental health center administrators), half of which will occur upon completion of the open trial and half of which will occur upon completion of the pilot randomized trial. In order to be eligible to participate in this interview, individuals must be: 18 years or older, currently employed in one of the stakeholder settings described above, able to speak English sufficiently well to participate in the interview, and to consent to participate in the interview.

Special classes. Because the purpose of this study is to develop and evaluate the feasibility and acceptability of CARE in prisoners during the vulnerable period of community re-entry, it is necessary to sample a prison population. Prisoners are an understudied population with complex treatment needs; hence the urgency for more research attending to the mental health concerns of this population. Incarcerated children 18-21 will be eligible. Recruitment procedures are described in more detail in the "Protection of Human Subjects" section.

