### **3.b.4. Potential intervention issues.**

Telephone access: Our research and others has shown that telephone interventions are feasible and acceptable for individuals with SMI and for justice involved persons (see prelim studies). A minority (< 10% at our recruitment site based on previous experience) may not have regular access to their own telephone, but have been able to provide a phone number for a family member or other locator that is accessible to them for use upon re-entry; reliance upon these contact methods is feasible.

Significant others: Some patients may have difficulty identifying a family member or SO for study participation. Thus, our definition will be broad. For example, if there is no local SO available, we may identify an SO who is geographically distant, but otherwise available to participate in phone sessions. We may also consider inclusion of an alternative support person (e.g., case manager) who is willing to

participate if no family member or close friend is willing/able. If a participant has no SO available, we will omit this portion of the intervention. However, we will allow for the participation of an SO later in treatment, should one become available. Although we expect the family component of the intervention to be feasible, given our previous experience with prisoner re-entry, assessing its feasibility/acceptability in the context of CARE will be part of the proposed study. In our previous studies with prisoners, 10-15% of participants have been unable to identify an SO.

Patient-SO conflict: In situations of mild-moderate relationship impairment, we will carry out CARE as outlined and identify relationship issues as one additional risk factor to be addressed. We will then engage the patient and the SO in problem-solving to determine what to do about their relationship issues (e.g., referral to marital/family treatment). In a minority of cases, there may be such severe impairment and/or abuse that facilitating increased involvement is not clinically appropriate. As in our previous studies of re-entering prisoners, we will work with the participant to identify another SO for participation and we will privately provide information about partner violence resources to participants as needed (see Human Subjects).

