SO participants: Once participants have been determined to meet eligibility criteria through study assessment, and have completed 2 of the 4 individual sessions with their CARE counselor, the CARE counselor will work collaboratively with the participant to identify an appropriate SO for participation. In addition to the standard inclusion criteria described above, for those participants recruited while in prison, we will require that this individual be on the patient's approved visitor list at the [REDACTED] for both practical (i.e., in order to attend the family/SO session prior to release) and also safety (i.e., because this person will have been cleared by the [REDACTED] for entry) purposes. With written permission from the participant, the CARE interventionist will contact the SO over the telephone to describe the program and to explain all aspects of the study to the potential SO, including the risks and benefits, and invite him/her to attend the family session. The family session may occur either prior to release in prison, or after release in the community. If the session occurs after release from prison, the session may take place either by telephone, by zoom, or in person (e.g. our offices or a residential facility, with their approval). Immediately prior to the family session, a study RA will meet the SO in person to obtain the SO's written consent for participation, following our standard informed consent procedures as described above. If the family session will take place by telephone or zoom, a waiver of documentation of consent will be utilized for the SO. The research presents no more than minimal risk of harm to subjects and involves no procedures for which written consent is normally required outside of the research context since the SO is only participating in a family session and brief phone sessions to support the participant. SOs are not completing any assessments nor is the treatment focused on the SO. We will try to consent SOs in person whenever possible. When a waiver of documentation of consent takes place, a study RA will send a copy of the consent form to the SO and then review it together during a telephone or zoom call, which will take place after the initial recruitment call. The SO will provide the RA with verbal consent over the phone or zoom and the RA will document this on a blank consent form. These forms will be filed with the other SO consent forms in a locked file cabinet in our offices.

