Secondary Outcomes: Using multilevel modeling of group by time, we will calculate the effect sizes and 95% CIs for: (1) percent time suicidal, as assessed by the LIFE, (2) alcohol and drug use severity using the AUDIT and DUDIT, respectively, and (3) overall functioning, employment stability, and housing stability, using the SF-12, JSI, and HSS, respectively. All assessments will use baseline scores, including percent time suicidal in the 90 days prior to study enrollment, as covariates. Potential group differences in rate of re-arrest will be calculated using simple chi-square analysis.

Target engagement/mechanisms of action. In this study, we will explore potential group differences in CARE's purported mechanisms of action. To that end, we will rely upon multilevel modeling of group

by time to calculate effect sizes and 95% CIs for change in VLQ, NIH Toolbox Instrumental Support, MSPSS, THI, and BARS scores across study time points. Across the four assessment time points, we will also evaluate associations between change in these intermediary constructs and primary/secondary outcome measures, using multilevel models.

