### **3.c.1. Inclusion of Women and Minorities**

Because the purpose of this application is to develop and pilot an intervention for prisoners with bipolar disorder (BD) around the period of community re-entry, the study population will consist of sentenced male and female inmates who meet criteria for BD. The study sample will also include participating family members/significant others (SOs). Equal numbers of male and female prisoners and SOs will be recruited.

Extant data from prisoners at participating facilities in [REDACTED] have been used to estimate the racial and ethnic distribution of the 104 participants (52 prisoners; 52 SOs) in the open and randomized trials. For females, the overall racial distribution will be approximately 66% White, 17% African American, 2% Asian, 4% American Indian or Alaska Native, and 11% other. The overall ethnic distribution for women will be approximately 17% Hispanic or Latina and 83% Non-Hispanic or Latina. For males, the overall racial distribution will be 48% White, 28% African American, 2% Asian, 4% American Indian or Alaska Native, and 18% other. The overall ethnic distribution for men will be approximately 24% Hispanic or Latino and 76% Non-Hispanic or Latino.

If the minority distribution of our participants falls below the targeted minority distribution (i.e., if

halfway through the study, the proportions of African Americans or Hispanics recruited are less than two thirds of the proportion of that minority distribution for the [REDACTED], then we will conduct additional outreach to the group that fell below their targeted enrollment numbers. We will also attempt to obtain feedback on why individuals for that group may refuse to participate in the study. Based on the feedback, we will take corrective action. All subjects will be asked to identify their race and ethnicity separately, by self-report, at the time of study entry, when demographic information is collected. We plan to conduct analysis to determine whether minority status is associated with any of the treatment utilization or clinical outcome data collected as part of this investigation.

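### Follow-up RAs are to be blind to arm, but significant-other consent taken by a study RA and an unstated interview order leave ways for the arm to become known before the LIFE is rated

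*Combined protocol and SAP*

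**What the plan says.** Section 3.c.5 makes the blinding commitment: "RAs complete follow-up assessments and will be blind to intervention condition". No procedure for keeping the blind follows. The only other mention of blinding, in section 3.b.3, concerns the rater of therapy fidelity, not outcome assessment.

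On SO consent, section 3.b.5 reads "Immediately prior to the family session, a study RA will meet the SO in person to obtain" written consent; where the session is by telephone or zoom, a study RA again handles it. Before that, "the CARE interventionist will contact the SO over the telephone to describe the program and to explain all aspects of the study". Section 3.b.1 offers SO participation only to those assigned to CARE, 12 in the open trial and 20 in the randomized trial: "Hence, we will enroll up to 32 SOs into this study".

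On interviews, section 3.c.5 names the LIFE and the THI among the instruments RAs are trained to give. Table 2 in section 3.b.8 puts both at baseline, pre-release, 1 month and 6 months; participants enrolled after release have no pre-release visit. The Brief Adherence Rating Scale (BARS), also an interview, follows the same schedule. Two satisfaction questionnaires and an Exit Interview are added at 6 months. The order of instruments and the person who conducts the Exit Interview are not stated.

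Section 3.b.9 takes percent time symptomatic (primary clinical outcome) and percent time suicidal (secondary) from the LIFE. It also compares the arms on "change in VLQ, NIH Toolbox Instrumental Support, MSPSS, THI, and BARS scores across study time points".

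**The concern.** The LIFE is rated by an interviewer, so its protection against expectation bias depends on the interviewer not knowing the arm. The plan asserts that state in one sentence, while other sections give RAs tasks that can disclose the arm. If an RA who knows the arm rates the LIFE, the group difference in percent time symptomatic or percent time suicidal could move in either direction, and nothing would be on record to show it.

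There is also a feasibility cost. Section 3.b.9 makes feasibility of the research procedures a primary goal, and section 3.c.9 presents the pilot as groundwork for a larger trial. The feasibility measures listed in section 3.b.9 do not include whether the blind was kept, so the pilot would not show whether the larger trial can rely on it.

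**Working it through.** The plan gives no figure on blinding and no sample-size calculation, so there is nothing to reproduce. The check sets the sections side by side.

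**Route 1: SO consent.**

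1. SOs belong to CARE only (section 3.b.1). Section 3.b.5 agrees: the SO is identified after two sessions with the CARE counselor.
2. E-TAU appointments are research assessments only (section 3.b.6).
3. From 1 and 2, an RA who consents an SO in the randomized phase knows that this participant is in CARE. In the open trial everyone receives CARE, so the point does not arise there.
4. The ideal schedule in section 3.b.6 puts sessions 1 and 2 in one week, session 3 in the next, and the fourth or SO session in the week after that. The consent can therefore come before the 1-month and 6-month LIFE.
5. The LIFE is compromised only if that same RA later rates that participant. Section 3.b.5 neither requires this nor rules it out.

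Ceiling on SO consents in the randomized phase:

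- CARE arm: 20 (section 3.b.1). E-TAU: 0.
- Section 3.b.4 reports that in previous studies "10-15% of participants have been unable to identify an SO". Then 20 × (1 − 0.10) = 18 and 20 × (1 − 0.15) = 17.
- SO participation is optional, so the true number may be lower.

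**Route 2: treatment questions at the same visit.**

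1. RAs are trained in the LIFE and the THI, and the two share every follow-up visit.
2. Section 3.b.2 says treatment utilization is assessed in both arms at each time point. Nothing says that CARE contacts are left out.
3. With no order stated, a participant may mention CARE contacts before the LIFE is rated, or at one visit before a later LIFE by the same RA. At 6 months the satisfaction measures and Exit Interview could do the same.
4. Such a mention is a cue, not proof. Other treatment is unrestricted in both arms (section 3.b.2), and CARE counselors work in the services that re-entering people use (sections 3.b.2 and 3.b.3), so E-TAU participants may also report seeing counselors.

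**Scale, by assumption only.** With 20 per arm, full follow-up and no covariate adjustment, the standard error of a difference in SD units is √(1/20 + 1/20) = 0.316. The 95% CI half-width is 1.96 × 0.316 = 0.62 SD (0.64 SD with t on 38 df). If biased rating shifted the difference by b SD, coverage would be Φ(1.96 − b/0.316) − Φ(−1.96 − b/0.316). This gives about 94% for b = 0.1, 90% for b = 0.2 and 84% for b = 0.3. The values of b are illustrative; the documents give no basis for any of them.

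**SO counts.** Section 3.b.1: 12 + 20 = 32. Section 3.c.1 speaks of "the 104 participants (52 prisoners; 52 SOs) in the open and randomized trials", where 12 + 40 = 52 prisoners. The difference, 52 − 32 = 20, equals the size of the E-TAU arm (40 − 20).

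**The case against.** The strongest reply is that no contradiction exists. Section 3.b.5 says an RA, not the participant's assessor. The blinding rule can be read as already barring an RA who consented an SO from rating that participant. The reference in section 3.c.5 to "random inspection of the completed forms by one of the research assistants" implies more than one RA, so separation is possible. Procedures may also exist in a manual that was not published, although section 3.c.6 mentions the manual only for adverse-event definitions. Much of this stands: a reader might infer that the plan contradicts itself or that blinding will fail, and the documents support neither. What remains is that the separation is left to inference rather than written into the step that discloses the arm.

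On route 2, the THI is not reproduced, so whether it would elicit CARE contacts is unknown. That is fair, and it is why this route is called possible. It is also true that rating the LIFE first protects only the visit at which disclosure occurs, and that asking for an arm guess at every visit could prime later ratings. The fix allows for both.

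The self-report QIDS and ASRM, and the monthly audio reliability checks, are partial cross-checks. But the self-report scales are exploratory and completed by participants who know their arm, and the plan does not say whether the reliability checker is masked.

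A reader might take the mismatch between 52 and 32 SOs as further evidence against the blind. It is not. The 52 sits in an enrollment estimate by race and ethnicity, and if SOs were in fact enrolled in both arms, route 1 would weaken. It is a separate count to reconcile.

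**Conclusion.** The point holds as a gap in procedure. In the randomized phase, SO consent by an RA discloses the arm to that RA; this rests on SOs being limited to CARE, as sections 3.b.1 and 3.b.5 say. The harm is conditional on the same RA rating that participant's LIFE. The THI and the 6-month measures are a second, uncertain route.

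The size is unknown. The 17 to 18 (at most 20) is a ceiling on SO consents, and it would be wrong to read it as the number of participants whose ratings are biased. Importance is limited: feasibility and acceptability are the primary goal, outcomes are reported as effect sizes with 95% CIs, and section 3.b.9 reads the effect sizes together with larger trials in related fields. The point still deserves a change, because two outcomes, including the primary clinical one, depend on the LIFE and the remedy needs little.

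**What to change.** 1. In section 3.b.5, have SO consent taken by existing staff who already know the arm, or by an RA who does no follow-ups for that participant.
2. At each visit, complete the LIFE mood and suicidality ratings before the THI, BARS, satisfaction measures and Exit Interview. Because this protects that visit only, give later LIFEs to another RA after any unblinding, where a second RA is already available.
3. Ask participants not to volunteer their assignment during the LIFE, and state that distress, safety concerns and adverse events may be reported at any time.
4. Log any unblinding when it occurs. Record the RA's guess of arm once, after the final (6-month) LIFE. Report both as a feasibility result.
5. If the THI would count CARE contacts, record these from study logs and analyse non-study treatment separately. Otherwise the THI comparison between arms would partly reflect delivery of the intervention itself.

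The cost is a fixed instrument order, a short instruction to participants, one form item and minor scheduling. Separately, reconcile the SO numbers in sections 3.b.1 and 3.c.1.

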### **3.c.6. Safety Monitoring Plan**

[REDACTED] will be responsible for overseeing the safety of all participants. [REDACTED] (who maintains her clinical license in RI) will be available to serve as clinical back-up for [REDACTED], when required. [REDACTED], study co-investigator, is a board-certified psychiatrist who will serve as the medical advisor. Participant safety will be monitored in two ways: (a) during the intake or ongoing assessments by the research staff, or (b) during intervention sessions. Research assessments will be conducted in the prison at study intake, at pre-release (4-10 weeks later), and in the community at 1 and 6 months post-release. We will monitor all participants for significant suicidal ideation (SI), homicidal ideation (HI), and clinical deterioration at each time point.

**During incarceration** the [REDACTED] standards for mandatory reporting of suicide risk specify that we are required to report anyone who has had suicidal ideation within the past 24 hours (as determined by a QIDS item 12 score > 1, LIFE PSR > 2, or reporting any current desire to hurt oneself to any member of the research staff). If the participant reports this level of SI within the past 2 weeks, but not in the 24 hours prior to the assessment, a voluntary referral will be offered. Participants meeting the prison's SI mandatory reporting criteria (or those who elect the voluntary referral) will be referred to a prison mental health clinician for evaluation, who will follow prison procedures. Standard prison procedures include: (1) checking in the prison's electronic medical record to see if the person has already been flagged as having SI; (2) having a licensed mental health clinician check in with the person and do a suicide risk evaluation; and/or (3) if needed, putting the person on psychiatric observation within the prison. If the prison mental health professional determines that someone's risk has gone down, that person will leave

psychiatric observation and return to the general population. All of these procedures are set and executed by the prison, which follows its own ethical and legal requirements. We will clearly describe this in our consent form. Homicidal risk will be defined by reporting any desire to hurt another person or member of the study staff. Standard mandatory reporting procedures (e.g., contact prison mental health staff) will be followed. Clinical deterioration will be defined using the QIDS (for depression) and ASRM (for mania) questionnaires at each assessment time point. Clinical deterioration for depression will be defined as a QIDS score of  $\geq 16$ . Clinical deterioration for mania will be defined as an ASRM score  $\geq 8$  (threshold for suspected hypo/mania). If someone meets these criteria for clinical deterioration while still incarcerated, a referral will be made to the prison's mental health staff, who will follow procedures similar to those described for suicide risk management above. Additionally, if a participant reports any escape plans, any sexual contact with anyone while incarcerated, or any ongoing child or elderly abuse or neglect, we are required to report this information to the [REDACTED]

**During the post-release period (in the community),** definitions of suicide risk, homicide risk, and clinical deterioration will be the same those described above; however, we will rely upon our standard study procedures (vs. [REDACTED] mandatory/voluntary reporting criteria) to facilitate clinician referral and safety assessment, as needed. If any study staff member identifies an individual with significant clinical deterioration or who report any suicidal or homicidal ideation in the course of standard assessment procedures, the staff member will immediately contact [REDACTED] (or the licensed covering clinician). The covering clinician will evaluate the participant over the telephone, by zoom, or in person. First, they will conduct a suicide and homicide risk assessment to determine whether it is necessary to take immediate action to prevent the participant from causing harm to self or others. If needed, actions that the covering clinician may take include escorting the person to the emergency [REDACTED] at [REDACTED] (if the person is in our offices), having a family member transport the person to [REDACTED] or another hospital, or calling the local police who may conduct a welfare check and evaluate the need to transport an individual to the closest emergency room for further evaluation.

If a study participant has experienced significant deterioration, but is not in immediate danger to self or others, we will take the following actions. First, we will inform the participant about procedures for contacting emergency services should they find themselves at risk for self-harm. Second, with the participant's knowledge and release of information, we will contact their community psychiatric or primary care providers to inform them of the deterioration. We will urge the participant to make an appointment with their outpatient provider(s); if they are not in active treatment with an outpatient provider, referrals will be provided. Third, and consistent with the CARE protocol, we will speak with the participant's SO so that he/she can be aware of the seriousness of the patient's symptoms and the agreed-upon treatment plan.

The study will rely upon the NIH's definitions for Common Adverse Events (AEs) and Serious Adverse Events (SAEs) for clinical research, and definitions will be operationalized in the approved study protocol document and manual of procedures (MOP). We will require that all study staff, study interventionists, and study participants report any adverse events to [REDACTED] immediately. These include, but are not limited to, psychiatric hospitalization and/or suicide attempt. Consistent with procedures utilized in our other psychosocial treatment studies for prisoners, jail detainees, and other high risk psychiatric samples, [REDACTED] will be available by telephone, by zoom, or in person during all participant assessments in the event that immediate consultation is needed for an emergent mental health or other problem. If an AE occurs, [REDACTED] will complete an Adverse Event form and report the event to the [REDACTED] IRB per their reporting guidelines and timeline. [REDACTED] will also review the adverse event form with the investigator team. They will gather any information needed to investigate the event and to determine subsequent action; this will also be reported to the IRB. We will inform NIH of any significant action taken as a result of any adverse event report. Anticipated and less serious adverse events will be submitted annually in reports to the IRB.

